Title: Treatment of Pressure Ulcers using Biological Skin Substitutes: A Comparison of Type-I Collagen and Amnion/Chorion Membranes

NCT: NCT06853210

Date: 26/07/2025

Background

Pressure ulcers, also known as decubitus ulcers or bedsores, are localized injuries to the skin and underlying tissue resulting from prolonged pressure. They are prevalent in individuals with limited mobility, such as the elderly and those with spinal cord injuries, particularly in long-term care settings. Effective management of pressure ulcers is crucial to prevent complications and improve patient outcomes, includes pressure relief, wound care, and advanced therapies such as bioengineered skin substitutes. Management of pressure sores is crucial due to their association with increased morbidity, healthcare costs, and reduced quality of life. This study aims to evaluate the efficacy of two treatment modalities: Type-I Collagen-based Skin Substitute (HPTC) vs. Dehydrated Human Amnion/Chorion Membrane (dHCAM) in promoting the healing of pressure ulcers. While both products are used in wound management, direct comparative studies evaluating their efficacy in treating pressure ulcers are limited.

MATERIALS AND METHODS

This prospective, randomized, controlled, open label, two parallel group, single-centre clinical trial will be conducted at a tertiary care hospital, in India, specializing in wound care and reconstructive surgery. The study protocol was approved by the Institutional Ethics Committee (Approval Number: AIMS/IEC/012/2025) and pre-registered with the ClinicalTrials.gov (NCT06853210). All procedures will be performed in accordance with the Declaration of Helsinki and Good Clinical Practice guidelines. All participants or guardians will be provided informed consent.

Outcome Measures

Primary Outcome:

- a. Percentage Wound Area Reduction.
- b. Histopathological Parameters
 - i. Vascular Infiltration
 - ii. Neo-epithelialization
 - iii. Fibroblast Activity
 - iv. Capillary Density
 - v. Inflammatory Response
 - vi. Collagen Deposition

Secondary Outcomes:

- a. Complete Wound Closure Rates (defined as 100% epithelialization).
- b. Wound Size Progression Over Time 7 weeks

- c. Number of Reapplications
- d. Incidence of treatment-related adverse events (e.g., infection, allergic reactions)
- e. Quality of Life Improvement
- f. Patient Satisfaction Scores

Study Design

Prospective, randomized, controlled, single-centre study with two parallel-group, open-label trial Duration: 6 weeks of intervention with follow-up for 1 week. Participants will be randomly assigned in a 1:1 ratio to receive either HPTC or dHCAM treatment

Sample Size: 80 patients (40 per arm)

- i. Group A: 20 patients receiving HPTC treatment.
- ii. Group B: 20 patients receiving dHCAM treatment.

Eligibility Criteria

Inclusion criteria

- a. Subjects must be at least 18 years of age or older
- b. Presence of a Stage III or Stage IV pressure ulcer, as defined by the National Pressure Ulcer Advisory Panel
- c. Ulcer size between 5 cm² and 25 cm²
- d. Ulcer duration of at least 4 weeks prior to enrolment
- e. The subject must agree to attend the twice-weekly/weekly study visits required by the protocol
- f. The subject must be willing and able to participate in the informed consent process
- g. Adequate blood supply to the affected area, confirmed by clinical assessment

Exclusion criteria

Potential subjects meeting any of the following criteria will be excluded from enrolment.

- a. A subject known to have a life expectancy of <6 months
- b. Presence of infection in the ulcer requiring systemic antibiotics.
- c. Known allergy to components of HPTC or dHCAM.
- d. Participation in another wound care study within the last 30 days.
- e. A subject with autoimmune or connective tissue disorders.
- f. Women who are pregnant or considering becoming pregnant within the next 6 months and those who are breast feeding.
- g. History of autoimmune disease, immunosuppressive therapy, malignancy, or uncontrolled diabetes (HbA1c >10%).

Study treatment

The treatment phase will begin with a series of assessments designed to confirm the patients' continued eligibility. Subjects who continued to meet study inclusion criteria after the screening period were randomized to one of two groups:

- 1. HPTC
- 2. dHCAM

Interventions

Wound Preparation - Prior to application, wounds will be debrided to remove necrotic tissue and cleansed with a standard saline solution.

Application Protocol:

- a. HPTC Group: Participants will receive standard wound care plus application of HPTC
- b. dHCAM Group: Participants will receive standard wound care plus application of dHCAM

All participants will receive standard care measures, including:

- a. Regular repositioning to alleviate pressure.
- b. Nutritional support to address deficiencies.
- c. Management of comorbid conditions.

Randomization and Blinding

Patients will be randomized 1:1 to the HPTC or dHCAM group using a computer-generated randomization sequence. Due to the nature of the interventions, blinding of participants and clinicians is not feasible. However, outcome assessors and data analysts will be blinded to group assignments.

Data Collection and Monitoring

- a. Baseline data: Demographics, medical history, ulcer characteristics.
- b. Weekly follow-ups: Wound measurements (photographic documentation), assess healing progress, record adverse events and patient-reported outcomes.
- c. End-of-Study Visit (Week 5): final wound assessment, collect patient feedback on treatment experience.
- d. Data entry and monitoring will be managed using an electronic data capture system.
- e. Regular monitoring will ensure adherence to the study protocol and address any compliance issues.

Statistical Analysis

Descriptive statistics for baseline characteristics. Statistical analysis was performed using SPSS version 26.0 (IBM Corp., Armonk, NY). Continuous variables were presented as mean \pm standard deviation or median (interquartile range) based on distribution normality assessed by Kolmogorov-Smirnov test. Categorical variables were presented as frequencies and percentages.

Between-group comparisons for continuous variables were performed using independent t-test or Mann-Whitney U test as appropriate. Chi-square test or Fisher's exact test was used for categorical variables. Time-to-event analysis was performed using Kaplan-Meier survival curves with log-rank test. Repeated measures ANOVA was used to analyse wound size changes over time.

Statistical significance was set at p<0.05. All analyses were performed on intention-to-treat basis with last observation carried forward for missing data.

Sample Size Calculation

Sample size calculation was based on expected difference in wound closure rates between groups. Assuming 85% closure rate in HPTC group versus 65% in dHACM group, with 80% power and 5% significance level, 38 patients per group were required. To account for 10% dropout rate, 40 patients per group were enrolled.

Study completion

Patients will complete the study 6 weeks after the first treatment visit. In addition, if, patients whose study ulcer closes prior to the 6-week visit will be considered as having completed the study. Complete healing of the study ulcer is defined as 100% re-epithelialization without drainage. At any point during the treatment period, patients can refuse to participate or withdraw from the study without prejudice. If a patient withdraws from the study, their last available wound measurement will be carried forward and used to calculate change in wound size and their final outcome

Ethical Considerations

- i. Approval will be obtained from the Institutional Ethics Committee.
- ii. Adherence to the Declaration of Helsinki and Good Clinical Practice (GCP) guidelines.
- iii. Informed and written consent will be obtained from all participants.
- iv. Adverse events will be monitored and reported.
- v. Participants may withdraw at any time without penalty.
- vi. Dissemination of Results
- vii. Findings will be submitted to peer-reviewed journals and presented at relevant conferences.

Timeline

Recruitment: 1 months Intervention: 3 months

Data analysis and reporting: 1 months

Potential Implications

This study aims to provide direct comparative data on the efficacy of HPTC versus dHACM in the treatment of pressure sores. The findings could inform clinical decision-making and potentially lead to improved patient outcomes in wound care management of pressure sores.

References:

- 2. Berhane, C. C., Brantley, K., Williams, S., Sutton, E., & Kappy, C. (2019). An evaluation of dehydrated human amnion/chorion membrane allografts for pressure ulcer treatment: a case series. *Journal of Wound Care*, 28(Sup5), S4–S10. https://pubmed.ncbi.nlm.nih.gov/31067170/
- 3. Vecin, N. M., & Kirsner, R. S. (2023). Skin substitutes as treatment for chronic wounds: current and future directions. *Frontiers in Medicine*, 10, 1154567. https://www.ncbi.nlm.nih.gov/pmc/articles/PMC10498286/
- 4. Helicoll® Clinical Study Publications. [https://helicoll.com/clinical-studies/]
- 5. A Randomized Controlled Clinical Trial Comparing the Use of High-Purity Type I Collagen Matrix (HPTC) and Dehydrated Human Amnion/Chorion Membrane (dHACM) Allografts in the Management of Diabetic Foot Ulcers.

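### Seven primary outcomes, six of them histological, are each tested at 5% with no multiplicity rule, and the histology has no stated sampling visit and no usable missing-data rule

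*Combined protocol and SAP*

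**What the plan says.** All references are to the combined protocol and SAP.

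- **Outcome Measures.** Primary outcome (a) is "Percentage Wound Area Reduction". Primary outcome (b) is "Histopathological Parameters", with six items: vascular infiltration, neo-epithelialization, fibroblast activity, capillary density, inflammatory response and collagen deposition. No order or hierarchy is given.
- **Data Collection and Monitoring.** Three entries say what is collected and when: "Baseline data: Demographics, medical history, ulcer characteristics"; "Weekly follow-ups: Wound measurements (photographic documentation), assess healing progress, record adverse events and patient-reported outcomes"; and "End-of-Study Visit (Week 5): final wound assessment, collect patient feedback on treatment experience". None names a biopsy, tissue sample or histology reading.
- **Interventions.** The only tissue removal mentioned is debridement before application. Nothing is said about keeping that tissue for histology.
- **Statistical Analysis.** Significance is p<0.05 throughout, with no adjustment or testing order. On missing data: "All analyses were performed on intention-to-treat basis with last observation carried forward for missing data".
- **Study completion.** On early closure: "patients whose study ulcer closes prior to the 6-week visit will be considered as having completed the study". For withdrawals, this section describes carrying forward a wound measurement only.
- **Sample Size Calculation.** Closure is assumed to be 85% with HPTC and 65% with dHACM, at no stated time point, with 40 enrolled per group. Study Design gives 40 per arm and, just below, 20 per group.

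**The concern.** There are two linked problems.

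The first is multiplicity. With seven co-listed primary outcomes and one unadjusted threshold, a report could claim a positive primary result on a single histology item while wound area shows no difference. Nothing in the plan holds the overall error rate at 5%.

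The second is that the six added outcomes may not be comparable between arms. The plan does not say when tissue is taken, how it is scored or who reads it. If it is taken late, patients who have closed and been counted as complete may contribute none. Whether a value is missing would then depend on a post-randomisation outcome that the plan expects to differ by arm. Neo-epithelialization shows this most clearly. Complete healing is defined by full re-epithelialization, so losing closers removes the best values, and more of them from the arm that heals better. Carrying values forward cannot repair this. No earlier histology value is listed, and if a baseline sample did exist, a pre-treatment value would enter the endpoint.

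**Working it through.** **The plan's own figure.** There is none for histology or for the overall error rate. The only stated sample size, 38 per group, is for closure. It is not reproduced by a standard two-proportion calculation for 85% against 65% at 80% power (73 per group two-sided, 57 one-sided). That is a separate defect, and nothing below depends on it.

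**Step 1: number of primary tests.** 1 wound-area outcome + 6 histology parameters = 7.

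**Step 2: chance of at least one false-positive primary result, each test at 0.05.**
- Independent tests: 1 − 0.95^7 = 1 − 0.698 = 0.302.
- Upper bound under any dependence: 7 × 0.05 = 0.35.
- The six histology items alone, if independent: 1 − 0.95^6 = 0.265.

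Positive correlation, plausible for items such as vascular infiltration and capillary density, brings the figure below 30%. The documents give no correlations.

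**Step 3: how many patients could supply tissue.** Inputs are 40 per arm and closure of 85% (HPTC) and 65% (dHACM), before dropout. Let f be the share of closers lost before tissue is taken. The documents do not give f, so the whole range is shown.

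Patients left: HPTC = 40 × (1 − 0.85f); dHACM = 40 × (1 − 0.65f).

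Detectable difference in SD units (two-sided 5%, 80% power, normal approximation): (1.960 + 0.842) × √(1/n₁ + 1/n₂).

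| f | HPTC | dHACM | Total of 80 | Detectable difference (SD) |
|---|---|---|---|---|
| 0% | 40 | 40 | 80 | 0.63 |
| 25% | 31.5 | 33.5 | 65 | 0.70 |
| 50% | 23 | 27 | 50 | 0.79 |
| 75% | 14.5 | 20.5 | 35 | 0.96 |
| 100% | 6 | 14 | 20 | 1.37 |

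The gap between arms in the proportion missing is (0.85 − 0.65) × f, so up to 20 percentage points. With the conflicting figure of 20 per arm, the worst case is 20 × 0.15 = 3 and 20 × 0.35 = 7. The planned 10% dropout would lower these counts further.

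**Step 4: what the carry-forward rule can do for histology.**
- If no baseline or interim sample exists, as the visit list suggests, there is no value to carry.
- If an unlisted baseline sample exists, the carried value predates treatment and says nothing about its effect.

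An earlier on-treatment sample could be carried forward, but the plan lists none.

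**The case against.** A reader might infer something stronger: that the plan, followed as written, produces either no histology at all or a comparison among unhealed ulcers only, with 20 of 80 patients contributing. The documents do not support that.

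- No sampling time is stated, late or otherwise. A fixed mid-treatment sample, or one at closure, is not excluded.
- Study completion says that early closers have completed. It does not say that they miss a final assessment or sample. The share lost could be anywhere from 0% to 100%, and 20 of 80 is only the far end.
- The visit list is brief. It also omits the number of reapplications, a listed secondary outcome, so absence from it is weak evidence that nothing will be collected. On its own, the missing sampling schedule is missing detail.
- The 85% and 65% rates carry no time point, so they cannot be tied to week 6.

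The other side can also say that the plan never states that one significant outcome is enough. If all seven had to be significant, there would be no inflation. It can add that a stated sampling time, a blinded reader and a suitable missing-data method could repair the histology without demoting it.

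The points about sampling stand, and they limit the second problem to a conditional one. The point about the decision rule does not remove the first. The plan states neither rule, and seven separate tests at p<0.05 leave the any-one-will-do reading open. A better sampling plan would not change that.

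**Conclusion.** The concern holds in a limited form. The firm part is multiplicity: seven primary outcomes at 5% each with no control. The chance of at least one false-positive primary result is about 30% under independence, never more than 35%, and lower if the outcomes are positively correlated. This assumes that any single significant primary outcome could be claimed.

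It is also firm that the six histology outcomes have no named sampling visit and that the blanket carry-forward rule has no listed histology value suited to it.

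Outcome-dependent loss of tissue is conditional on late sampling and on closers giving none. Its size runs from no loss to 6 and 14 patients left at 40 per arm (3 and 7 at 20 per arm). It rests on the plan's closure assumptions, taken to apply when tissue is collected. It would be wrong to conclude that histology could never serve as a primary outcome in this trial; the plan as it stands does not support that use.

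**What to change.** 1. Name percentage reduction in wound area as the single primary outcome; the weekly visits already measure the wound. Make the six histology parameters secondary or exploratory, with no confirmatory claim.
2. Take histology out of the carry-forward rule. Analyse only the samples obtained, and report their number by arm and by closure status. If sampling proves late, this remains a selected subset, which is why no confirmatory claim should rest on it.
3. State when samples are taken, how they are scored and who reads them. Whether and when to sample is for the sponsor; no additional biopsies are proposed.
4. Reconcile the timing statements: end-of-study visit at week 5, completion at 6 weeks, 6 weeks of intervention plus 1 week of follow-up, and wound size progression over 7 weeks. Reconcile 20 and 40 per arm as well.
5. Update the registry entry to match, and date the change relative to enrolment and to any review of outcome data. The sample size text already speaks of patients as enrolled, so this date matters.

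**Cost.** Changes to the outcome list, the analysis text and the registry; no new procedures. Histology can no longer carry a primary claim, and a registered primary outcome is changed, which must be disclosed. The alternative of keeping all seven as primary under a Bonferroni level of 0.05/7 = 0.0071 would raise the detectable difference from 0.63 to 0.79 SD even with complete data at 40 per arm, and would leave the sampling and missing-data problems unsolved.

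### The only listed safety outcome is restricted to treatment-related adverse events, and in this open-label trial nobody is named to judge relatedness; compare all adverse events by arm instead.

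*Combined protocol and SAP*

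**What the plan says.** Under Outcome Measures, secondary outcome d is "Incidence of treatment-related adverse events (e.g., infection, allergic reactions"). It is the only safety item among the primary and secondary outcomes.

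Under Randomization and Blinding, the document states that "blinding of participants and clinicians is not feasible", but also that "outcome assessors and data analysts will be blinded to group assignments". It does not define the outcome assessors or say which outcomes they assess.

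Adverse events are collected more widely than they are compared. Under Data Collection and Monitoring, the weekly visits "record adverse events and patient-reported outcomes", with no limit to related events. Ethical Considerations adds: "Adverse events will be monitored and reported".

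The analysis text that would apply to outcome d is general: "Chi-square test or Fisher's exact test was used for categorical variables", and "Statistical significance was set at p<0.05". There are no relatedness criteria, no named judge and no adjudication step, and no listed outcome compares adverse events of any cause between arms.

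**The concern.** Randomisation makes the arms comparable for adverse events of any cause. It gives no such protection to a subset picked out after randomisation by a causality judgement, if that judgement may be made with knowledge of the product. Belief about either product could then shift the share of events called related in one arm.

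The population makes the judgement difficult. The ulcers are Stage III or IV, have been present for at least four weeks, and are debrided before application. An infection in such a wound has an obvious explanation other than the product, yet infection is the first example the outcome gives.

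Two things are at stake. Unequal attribution can produce a difference where the true event rates are equal, or remove one where they differ. Equal and unbiased attribution still shrinks the event count, and so the information, in the only safety comparison the plan lists.

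**Working it through.** **No figure in the plan to reproduce.** The document gives no adverse event rate, attribution share or safety power. Its one sample-size statement, "with 80% power and 5% significance level, 38 patients per group were required", concerns wound closure and does not enter here.

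**Inputs**
- Patients per arm: 40 (Study Design, Sample Size). The lines directly beneath it list 20 per group, so 20 is also run.
- Tests: Fisher's exact, and chi-square without continuity correction, at 0.05 (Statistical Analysis). Sidedness is not stated; two-sided is assumed.
- True event rates and shares called related: assumptions. Each patient has at most one event, and the share applies independently to each.

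**Formulas**
- Reported rate = true rate × share called related.
- Expected patients = 40 × reported rate.
- Chance of p<0.05 = sum, over all pairs of counts that the test rejects, of the product of the two binomial probabilities.

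**False difference: true rate 20% in both arms**
- Shares 50% and 50%: 0.20 × 0.50 = 10% in each arm. Half the events leave the comparison (4 of the 8 expected per arm).
- Shares 40% and 60%: 0.20 × 0.40 = 8%; 0.20 × 0.60 = 12%.
- Shares 40% and 80%: 8%; 0.20 × 0.80 = 16%.
- Shares 30% and 70%: 0.20 × 0.30 = 6%; 0.20 × 0.70 = 14%.

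**Masked difference: true rates 40% and 20%**
- Shares 35% and 70%: 0.40 × 0.35 = 14%; 0.20 × 0.70 = 14%. A 20-point difference disappears.

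| True rates | Shares called related | Rates compared | Expected patients of 40 | Chance of p<0.05, 40 per arm (Fisher / chi-square) | Same, 20 per arm |
|---|---|---|---|---|---|
| 20% v 20% | 50% v 50% | 10% v 10% | 4.0 v 4.0 | 2% / 6% | 1% / 4% |
| 20% v 20% | 40% v 60% | 8% v 12% | 3.2 v 4.8 | 4% / 10% | 2% / 6% |
| 20% v 20% | 40% v 80% | 8% v 16% | 3.2 v 6.4 | 11% / 21% | 5% / 11% |
| 20% v 20% | 30% v 70% | 6% v 14% | 2.4 v 5.6 | 11% / 24% | 5% / 11% |
| 40% v 20% | all events counted | 40% v 20% | 16 v 8 | 41% / 50% | 19% / 29% |
| 40% v 20% | 35% v 70% | 14% v 14% | 5.6 v 5.6 | 2% / 5% | 2% / 5% |

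The effect grows with the true rate. With 40 per arm, shares of 30% and 70% give a false positive by Fisher's test in 11%, 23% and 35% of trials at common true rates of 20%, 30% and 40%. Shares of 40% and 60% give 4%, 7% and 10%.

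**The case against.** A reader might infer that relatedness will be decided at the bedside by clinicians who know the product. The document does not say this. It names neither the person who records adverse events nor the person who judges them, and it blinds the outcome assessors. Treatment-related event incidence is a listed outcome, so those assessors may be meant to cover it. This objection stands against any assertion that attribution will be unblinded. It does not settle the matter, because the document does not assign the judgement to the blinded assessors either.

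A reader might also infer that unrelated events go unrecorded. That is wrong: adverse events are recorded weekly and are to be reported without a relatedness limit, so an all-cause comparison could be made from the data. What is missing is a listed outcome that makes it.

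The bracketed examples could mean that every infection counts as treatment-related by default. The wording allows that reading but does not establish it, and the ambiguity is itself a reason to reword.

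Finally, the sizes are assumed. Both arms receive an active skin substitute plus standard care, and nothing in the document shows that clinicians favour one. The numbers are small too: observed counts of 3 of 40 against 6 of 40 give a two-sided Fisher p of 0.48. All of this stands. It limits what can be said about size, but leaves the restricted outcome as it is.

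**Conclusion.** The point holds in this form: the plan's one safety outcome depends on a causality judgement whose owner, criteria and blinding are unstated, in an open-label trial, and no all-cause comparison is listed. That follows from the text alone.

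The size cannot be established. Every event rate and attribution share above is an assumption. On those assumptions a mild imbalance (40% versus 60%) matters little at a true rate of 20%. A large one (40% versus 80%) doubles the apparent rate in one arm, and an opposing one (35% versus 70%) can hide a true twofold difference. The documents do not show that biased attribution will occur, only that the plan does not exclude it. The loss of events from the comparison, by contrast, needs no bias.

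This is a secondary outcome in a trial whose sample size was not set for safety. The change is worth making because it is cheap; the point does not undermine the trial.

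**What to change.** Reword secondary outcome d as: *Incidence of all adverse events, and of all study-ulcer infections and local reactions, by randomised arm, irrespective of judged relationship to treatment.* Keep treatment-related events as a descriptive sub-listing, and state there who judges relatedness, by what criteria, and whether that person is blinded.

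The cost is one reworded outcome, one extra table and a sentence on adjudication. The weekly visits already record adverse events, so no new visit is needed. There are two downsides: background events unconnected with either product add noise to the comparison, and the headline adverse event rate will be higher. The rewording removes the causality filter but does not by itself ensure that events are detected equally in both arms, since the person recording them is also unnamed.

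### The stated total is 80 patients (40 per arm), but the two group lines directly below it give 20 each, so the enrolment target differs by a factor of two

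*Combined protocol and SAP*

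**What the plan says.** Under Study Design, the sample size entry reads "Sample Size: 80 patients (40 per arm"). The two list items that follow give the count for each group: "Group A: 20 patients receiving HPTC treatment" and "Group B: 20 patients receiving dHCAM treatment". Allocation is equal: "Participants will be randomly assigned in a 1:1 ratio to receive either HPTC or dHCAM treatment".

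The Sample Size Calculation section supports the larger number. It starts from closure rates ("Assuming 85% closure rate in HPTC group versus 65% in dHACM group"), continues "with 80% power and 5% significance level, 38 patients per group were required", and ends "To account for 10% dropout rate, 40 patients per group were enrolled".

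**The concern.** Two different enrolment targets stand in adjacent lines. The group lines add up to half of the headline total and half of what the Sample Size Calculation section asks for.

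Three things depend on this number: the length of the randomization sequence, the point at which enrolment ends, and the power that can be claimed. The plan has no interim analysis and no stopping rule, so the planned number alone defines a complete trial. A team working from the group lines could stop at 40 patients. With both figures in the record, stopping at 40 or at 80 could afterwards be described as planned. That matters more than usual here, because patients and clinicians know the assignments.

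**Working it through.** **Step 1: the counts.**

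| Place | HPTC arm | Amnion/chorion arm | Total |
|---|---|---|---|
| Study Design, sample size entry | 40 | 40 | 80 |
| Study Design, group lines | 20 | 20 | 40 |
| Sample Size Calculation | 40 | 40 | 80 |

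20 + 20 = 40, against 40 + 40 = 80, a ratio of 2. I looked for a reading in which both hold and found none. The design has two parallel groups with 1:1 allocation, and no section mentions a stage, stratum, biopsy subset or interim cohort of 20 per group. The lines are running text, so neither a broken table nor a redaction explains the difference.

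**Step 2: the plan's own calculation.** Inputs from the Sample Size Calculation section are p₁ = 0.85, p₂ = 0.65, 80% power and 5% significance. Sidedness is not stated, so I take two-sided. The mean proportion is 0.75.

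n per group = [1.960 × √(2 × 0.75 × 0.25) + 0.842 × √(0.85 × 0.15 + 0.65 × 0.35)]² / 0.20²
= [1.960 × 0.6124 + 0.842 × 0.5958]² / 0.04 = 1.7017² / 0.04 = 72.4, rounded up to 73.

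The stated 38 does not reproduce. Other two-sided variants give 70 (unpooled), 71 (arcsine) and 83 (continuity-corrected). One-sided variants give 55 to 67. Inflating 38 for 10% dropout gives 38 / 0.9 = 42.2, rounded up to 43, or 38 × 1.1 = 41.8, rounded up to 42, rather than 40. These are separate errors, shown here because they affect what each enrolment target delivers.

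**Step 3: power at each target.** The normal approximation is

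power = Φ{[0.20 × √n − 1.960 × 0.6124] / 0.5958}

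- n = 20: (0.8944 − 1.2002) / 0.5958 = −0.513, power 30.4%.
- n = 40: (1.2649 − 1.2002) / 0.5958 = 0.109, power 54.3%.

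The plan names both the chi-square and Fisher's exact test for categorical variables, so I also enumerated all outcomes exactly.

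| Per arm | Normal approx. | Chi-square, exact enumeration | Fisher | Normal approx., one-sided |
|---|---|---|---|---|
| 20 | 30.4% | 31.4% | 20.9% | 42.5% |
| 40 | 54.3% | 55.3% | 46.0% | 66.7% |

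**Step 4: precision.** The half-width of the 95% interval for the difference in closure is 1.96 × √[(0.1275 + 0.2275) / n].

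- n = 20: 1.96 × √0.01775 = 0.261, or 26.1 points.
- n = 40: 1.96 × √0.008875 = 0.185, or 18.5 points.

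**Step 5: effect detectable with 20 per arm.** Holding the HPTC rate at 85%, power is about 80% when the comparator rate is about 44% (79.7% by normal approximation, 81.2% by chi-square). With Fisher's test, power at that point is 71.7%, and the comparator rate has to be about 40% (79.7%). The detectable difference is therefore 41 to 45 points, against the 20 points the plan assumes.

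**The case against.** The strongest reply is that this is an evident slip and not a real choice between two targets. The figure of 40 per arm appears twice, and one of those places gives a derivation. The figure of 20 appears only in the two group lines and is derived nowhere. Nothing gives those lines precedence, and anyone who reads the Sample Size Calculation section has good evidence that 80 was meant. I accept this. It makes the ambiguity lopsided and points to the likely correction, but it does not remove the conflict from a controlling document.

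A second point also stands. Only the drop from about 54% to about 30% belongs to this inconsistency. The gap between the claimed 80% and the 54% available at 40 per arm arises because 38 per group does not follow from the stated inputs, and it would remain after the group lines are corrected.

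Finally, enrolment may already be over. The plan mixes future and past tense and does not settle the matter. If enrolment has ended, the record still needs to state which number was planned.

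**Conclusion.** The contradiction is real and must be corrected: the group lines give 40 patients where the headline and the calculation give 80. That conclusion rests on addition alone.

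If the group lines were followed, power for the assumed 20-point difference would be about 30% (21% with Fisher's test), compared with about 54% (46% with Fisher's test) at 40 per arm. The interval for the difference would widen from about ±18 to about ±26 points. These figures assume closure rates of 85% and 65%, a two-sided 5% test, and all randomized patients analysed. A one-sided test would raise both powers, to 42% and 67%, without closing the gap.

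The weight of the text favours 40 per arm as the intended number, but only the sponsor can confirm it.

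**What to change.** The sponsor should confirm the planned number and make every statement of it agree.

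- If the target is 40 per arm, change the Group A and Group B lines to 40 each. Do not let that edit imply that the 80% power claim is sound: at 40 per arm, power is about 54% under the plan's own assumptions, and the Sample Size Calculation section needs a separate correction.
- If the target is 20 per arm, change the total to 40, revise the Sample Size Calculation section to match, and restate power as about 30%.
- In either case, use the same number for the randomization list and as the point at which enrolment ends. If enrolment has already closed, state the number planned beforehand and the number actually enrolled.

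Reconciling the counts costs a two-line protocol correction if 40 per arm is confirmed. The 20-per-arm route also means revising the total and the calculation.
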